APPENDIX A: STANDARD OPERATING PROCEDURE (SOP A) SPECIMEN

HANDLING OF RADICAL PROSTATECTOMY SPECIMEN

RP specimen handling and reporting should be standardized to an extent that would serve the purposes of the study and minimize the need for re-evaluation of the histological glass slides afterwards.

In order to achieve modern standards of collecting biospecimens for further research use, the RP specimen should be transferred immediately to pathology department with shortest possible delay.

MACROSCOPIC INSPECTION PROSTATE

After macroscopic inspection, please

- a) Document the weight of the prostate and ink paint of the prostate and base of seminal vesicles. This means that the left and right side should be inked with different colors, (additional ink colors can be used for example in the anterior surface and in the surface facing bladder neck.)
- b) As appropriate, retrieve biobanking samples without compromising the diagnostics
- c) Dissect apex basis of the prostate using the cone method, (85) containing at least the base of the seminal vesicles, perpendicular to the urethra and section then sagitally parallel to the urethra. The remaining central part should be sectioned transversally, and preferably whole mounted to get the best discretion for positive surgical margins (PSM) and extra-prostatic extension (EPE). For the same reason, the entire prostate should be embedded.

The Gleason-grade evaluation shall be done in accordance with the guidelines published in(86-88). If an ePLND has been done, reporting the number of positive lymph nodes and the number of lymph nodes evaluated is essential. Side-specific report on lymph-node data is recommended but not compulsory.

The anatomy of the prostate capsule is not well defined, and histologically there is no continuous capsule surrounding the glandular structures. The discovery of cancer cells outside the contour of the prostate gland should therefore be reported as EPE instead of extra-capsular extension. The apical border of the prostatectomy specimen is more complex in terms of EPE as the glandular structures are mixed with the skeletal muscles of the urogenital diaphragm, and no identifiable capsule exists. EPE can be assessed as cancer in the inked apical margin. In practice, this is equal to positive surgical margin (PSM). Consensus recommendations state that EPE and its location should always be reported, either focal or non-focal (established, extensive). There are no objective criteria for the designation of the degree of EPE.

PSM is caused either by a true extension of cancer beyond the resection line to the extra-prostatic tissue or by an iatrogenic incision of capsule/intraprostatic tumor (i.e. pT2+ disease). The latter should not be interpreted as EPE. The predictive significance of PSM for disease recurrence is evident,(84,89-92) but there is only limited data available on the significance of PSM in predicting cancer-specific mortality.(91,92) Possible intraoperative violation to prostatic capsule should be recognized while handling the prostatectomy specimen. Consensus recommendations suggest that the extent of PSM should be indicated as focal or multifocal in nature. In addition, the anatomic location should be reported, as well as the length of PSM in millimeters. Finally, the pathology report should note whether PSM is in an area of EPE or if any possible non-repaired intra-prostatic and intra-tumor incision exists.

The pathological TNM stage of the tumor is an independent predictive factor.(16,93,94) Therefore, it should be included in the pathology report of prostatectomy specimens and the most recent version of the American Joint Committee on Cancer/International Union Against Cancer (AJCC/UICC) staging system should be used. In the current staging system, all cancers with EPE, regardless of location or extent, are staged as pT3a. There is, however, validated evidence on prognostic significance of EPE subdivision into

focal versus non-focal,(95,96) although the assessment of focal versus non-focal/extensive EPE per se lacks uniform consensus criteria.

Cancer invading the muscle wall of the seminal vesicle is considered as stage pT3b cancer. However, intraprostatic vesicular structures should not be taken into account while determining seminal vesicle invasion (SVI). Thus, SVI is always by definition EPE.

TABLE 1

Minimum requirements and suggested additional information for radical prostatectomy pathology report

Minimum standard requirements for reporting	Recommended additional information
cancer in a prostatectomy specimen	
1. Histological type of carcinoma	
2. Histological grade	
- primary Gleason pattern	- individual grading of separate significant cancer foci
 secondary Gleason pattern 	- tertiary pattern and its proportion, modified Gleason score
- total Gleason score	 percentage of Gleason 4-5 cancer
3. Surgical margin status	- extent of PSM: focal, multifocal
- location of PSM	- length of PSM in millimeters
	- PSM in the area of surgical incision (pT2+) or EPE
4. EPE	- site of EPE (basal, apical, lateral)
- focal	
- non-focal (extensive,	
established)	
5. Tumor quantization	
 proportion of prostate involved 	 prostate size and weight
by cancer	- dimensions (diameter in mm) and location of the dominant
	cancer nodule
6. Seminal vesicle invasion	
7. Pathological stage, pTNM	
 notification of the version of 	 number of total lymph nodes examined
AJCC/UICC staging system	 diameter of largest lymph node metastasis
- pT = primary tumor	Other pathologic findings (if present):
<pre>-pN = regional lymph nodes,</pre>	- perineural invasion
specify the number of positive	- treatment effect on carcinoma
nodes	- presence of high-grade PIN
- pM = distant metastasis	- inflammation

APPENDIX B: RADIATION TREATMENT

This protocol allows for the following treatment modality options:

- External beam radiotherapy (EBRT) only
- EBRT and high-dose rate (HDR) brachytherapy (BT) combined

RADIOTHERAPY PROTOCOL FOR EXTERNAL BEAM RADIOTHERAPY (EBRT)

FACILITY AND EQUIPMENT

- The treatment centre shall have equipment for and previous experience with Intensity Modulated Radiotherapy (IMRT) and/or Volumetric Modulated Arc Therapy (VMAT).
- The make and version of the particular treatment equipment shall be reported to the QA-centre.

PATIENT POSITIONING AND SIMULATION

- Pre-treatment preparation
 - \circ $\;$ The patient shall be immobilized with at least leg fixation.
 - Among patients treated with EBRT, the patient reference coordinate system shall be defined by using implanted fiducial markers in the prostate.
 - In patients with rectum diameter > 4 cm at the level of the prostate due to faeces or flatus, a new planning CT/MR should be considered after emptying the rectum.
 - The bladder filling protocol should be according to local guidelines with the aim to keep the bladder comfortably filled during the whole RT series with a volume as close as possible to the filling during the treatment planning CT/MR.
- Pre-treatment imaging
 - For structure delineation, CT and (preferably MR imaging) shall be performed with the patient in the treatment position in his fixation device on a flat tabletop.
 - \circ The CT (and MR scanning) shall be performed from L3 to the lower border of trochanter minor.
 - Slice-thickness shall be maximum 3 mm.
 - Treatment planning dose calculations shall be performed based on CT but can also be based on MRI if this technique is implemented and verified at the particular treatment centre. In case MRI based treatment planning and dose calculation is used, any pre-processing of the imaging data (e.g. conversion to appropriate radiation interaction data) shall be reported.
 - \circ $\;$ Image sets from the different modalities in treatment position shall be co-registered.
 - Reference imaging for IGRT shall be made with well-defined reference system based on the internal fiducials.

VOLUME SELECTION AND DEFINITION

- The recommendations made by ICRU shall be followed.
- The naming of target and organs-at-risk volumes shall follow the Santanam et al IJROBP 83(4): 1344-1349, 2012.
- Target volumes:
 - Clinical Target Volume(s):
 - Prostate (CTVT1) shall include the prostate and any potential extra-capsular tumor growth.

- Proximal seminal vesicles (CTVT2) shall include the proximal 2 cm of the seminal vesicles.
- In case of tumor involvement in the vesicle(s), the engaged vesicle(s) shall be outlined separately (CTVT3).
- Pelvic nodes (CTVT4) shall be delineated according to the RTOG guidelines.
- Planning Target Volume(s):
 - Prostate (PTVT1) consists of CTVT1 and a margin of 5-7 mm during the part of the treatment guided by the fiducials. During pelvic + prostate irradiation, where bone matching is used, a 10 mm isotropic margin should be applied to CTV_P.
 - **Proximal seminal vesicles (PTVT2)** consist of CTVT2 and a margin of 5-10 mm.
 - Tumor engaged vesicle(s) (PTVT3) consist(s) of CTVT3 and a margin of 5-10 mm.
 - Pelvic nodes (PTVN) consist of CTVN and an isotropic margin of 7-10 mm.
- Organs at risk (OARs)
 - The following OARs shall be delineated (structure name within parenthesis):
 - Rectum (Rectum), delineated according to the recommendations by QUANTEC¹: "The rectum should be segmented from above the anal verge to the turn into the sigmoid colon, including the rectal contents."
 - Anal canal (AnalCanal) shall be outlined as a separate volume
 - **The urinary bladder (Bladder)** shall be outlined as the outer contour of the bladder, i.e. including the muscle wall.
 - The penile bulb (PenileBulb) is defined as the oval-shaped area bounded by the crura, corpora spongiosum and the levator ani muscles (the most proximal portion of the penis) sitting approximately 1-1.5 cm caudal to the prostate. The penile bulb appears as a hyperintense oval-shaped structure on T2-weighted MR images and thus MR-based segmentation is recommended.
 - BowelBag is delineated from the level of 2 cm above the PTV-N, then drawing the whole intestinal cavity excluding muscles, vessels and internal organs (other than bowel) down to the most inferior small-or large bowel loop that is not rectum.
 - The femoral heads (FemoralHead_L and FemoralHead_R) are delineated circumferentially not including the femur neck.

PLANNING AIMS AND DOSE-VOLUME CONSTRAINTS

- Absorbed dose prescription
 - Fractionation schedules which equals to a biological equivalent of 2 Gy (BED2) to 78 Gy are allowed with dose prescriptions comparable to schedules given in Table 1. Hypofractionation schedules with fraction doses >2.5 Gy are not permitted within this protocol. Documented experience of hypofractionated schedules in published reports or quality registration is a requirement.
 - For treatment planning optimization, the physical objectives and constraints shall be prioritized according to the examples given in **Table 2**.
- Fractionation and treatment time
 - Radiotherapy shall be given daily, 5 days per week
 - The overall treatment time shall not exceed 4 days more than an optimal treatment schedule with 7 weekdays whereof 5 treatment days per week. In case of treatment time exceeding this recommendation, corrective compensation shall be made according to local practice.

¹ Michalski JM, Gay H, Jackson A, Tucker SL, Deasy JO. Radiation dose-volume effects in radiation-induced rectal injury. Int J Radiat Oncol Biol Phys. 2010 Mar 1;76(3 Suppl):S123-9. doi: 10.1016/j.ijrobp.2009.03.078.

TREATMENT PLANNING

- The radiation treatment shall be given with 6-18 MV x-rays and with IMRT/VMAT technique.
- Treatment planning technique, e.g. delineation of help structures, and machine dependent constraints, are according to each center's treatment planning manual.

DOSE COMPUTATION

- Maximum allowed voxel size for the dose calculation grid is 3 mm in the transversal plane. A size equal to the CT slice thickness is recommended.
- The make and version of the particular treatment planning system and dose calculation algorithm shall be reported.

TREATMENT VERIFICATION

- Image-guided treatment delivery
 - The position of the fiducials in the prostate shall be estimated based on electronic kV/MV portal imaging or cone beam CT.
 - The verification and correction shall be performed prior to every treatment fraction. The treatment should start as soon as readily possible after the verification/correction.
 - The monitor units (dose) used for verification of position should be considered and compensated for if MV portal imaging is used.

ADDITIONAL CONSIDERATIONS FOR COMBINED MODALITIES

- Drug therapy
 - EBRT should begin after 12 full weeks and preferably before 14 full weeks after the date of the first LHRH agonist injection.

QUALITY ASSURANCE

- Preparatory
 - Reference dosimetry shall be carried out according to IAEA, and verified through external dosimetry audits.
 - A dummy run shall be performed before including patients in the trial. It should include delineation of structures and dose planning.
- Pre-treatment patient specific QA
 - Individual case review shall be performed according to local practice of each centre.

Fractionation	Target	Number of	Dose per	Prescribed	(EQD2 ₃) (Gy)
schedule	structure	fractions	fraction (Gy)	total dose	
				(Gy)	
Α	PTVT1	39	2.00	78.0	(78.0)
Α	PTVT3	35	2.00	70.0	(70.0)
Α	PTVT2	25	2.00	50.0	(50.0)
Α	PTVN	25	2.00	50.0	(50.0)
В	PTVT1	29	2.50	72.5	(79.8)
В	PTVT3	29	2.30	66.7	(70.7)
В	PTVT2	29	1.80	52.2	(50.1)
В	PTVN	29	1.80	52.2	(50.1)
С	PTVT1	39	2	78	(78.0)
С	PTVT3	39	1.9	72,8	(70.0)
С	PTVT2	39	1.5	58,4	(50.0)
С	PTVN	39	1.5	58,4	(50.0)
D_SIB	ΡΤΥΤ	35	2.2	77.0	(78.0)
D_SIB	PTVN	35	1.6	56.0	(52.0)

Table 1. Dose prescriptions

In case of simultaneous integrated boost treatment (SIB) the treatment regime will be 2,2 Gy to the prostate (PTVT4) (BED2= 78 Gy, alfa/beta=3) and 1,6 Gy to elective LN (PTVN4) in 35 fractions (BED2= 52 Gy, alfa/beta=3 Gy).

CALCULATION FOR SIMULTANEOUS INTEGRATED BOOST (SIB)

Fraction dose [Gy] Nominal total dose for 35 f [Gy] EQD2 [Gy] ($\alpha/\beta = 3$ Gy) Pelvic Lymph nodes: 1,60Gy/35f Nominal dose 56Gy, EQD2 [Gy] ($\alpha/\beta = 3$ Gy) 52Gy Prostate and vesiculae seminales: 2,16Gy-2.2Gy/35f Nominal dose 76-77Gy, EQD2 [Gy] ($\alpha/\beta = 3$ Gy) 78-80Gy

 $Organs \mbox{ at risk and dose constraints for SIB 35f}$

Rectum: D5% < 72,7 GY, D20% < 68,9 GY, D50% < 59,1 GY, D60% < 49,3 GY. Not greater or less than 67,0 Gy to half of circumference and not greater or less than 49,3 Gy to entire circumference.

AnalCanal: not more than 67,0 Gy til half of circumference.

Bladder: D20% < 68,9 Gy, D50% < 64,0 Gy. Dmin (D100%) < 49,3 Gy.

FemoralHead: D50% < 49,3 Gy.

IntestinalCavity: D50% < 44,4 Gy.

BladderNeck Dmax < 72,8 Gy.

Table 2A. Dose prescription priorities for fractionation for schedule A

Priority	Structure	Prescribed	Dose-volume
		Dose (Gy)	recommendations
1	CTVT1 (Prostate)	78	D _{98%} ≥ 76 Gy (97%)
2	CTVT3 (tumor involved ves)	72.8	D _{98%} ≥ 70.7 Gy (97%)
3	PTVT1	78	D _{95%} ≥ 75 Gy (96%)
4	Rectum		V _{70Gy} < 20 %
5	PTVT1	78	D _{98%} ≥ 74 Gy (95%)
6	PTVT2	72.8	D _{98%} ≥ 68.8 Gy (94%)
7	CTVT2 (prox ves, 2cm)	58.4	D _{98%} ≥ 55.3.5Gy (95%)
8	CTVN (Nodes)	58.4	D _{98%} ≥ 55.3 Gy (95%)
9	Rectum		V _{75Gy} < 15 %
10	ΡΤVΤ3	58.4	D _{95%} ≥ 54.1 Gy (95%)
11	PTVN	58.4	D _{98%} ≥ 54.1 Gy (93%)
12	FemoralHeads_L/R		D _{2%} ≤ 51Gy
13	BowelBag		$V_{30Gv} < 300 \text{ cm}^3$
	-		$V_{40Gy} < 150 \text{ cm}^3$
			$V_{45Gv} < 100 \text{ cm}^3$
			$V_{50Gy} < 35 \text{ cm}^{3}$
14	Rectum		V _{60Gy} < 35 %
15	Body-PTV		D _{2%} ≤ 83 Gy (107%)
16	Bladder		D _{mean} ≤ 62 Gy (80%)

Table 2B. Dose prescription priorities for fractionation for schedule B

Priority	Structure	Prescribed	Dose-volume
		Dose (Gy)	recommendations
1	CTVT1 (Prostate)	72.5	D _{min} ≥ 68 Gy (97%)
2	CTVT3 (tumor involved ves)	66.7	D _{min} ≥61 Gy (97%)
3	PTVT1	72.5	D _{95%} ≥67 Gy (96%)
4	Rectum		V _{64Gy} < 20 %
5	PTVT1	72.5	D _{98%} ≥ 66 Gy (95%)
6	PTVT2	66.7	D _{98%} ≥ 59 Gy (94%)
7	CTVT2 (prox ves, 2cm)	52.2	D _{min} ≥43Gy (95%)
8	CTVN (Nodes)	52.2	D _{min} ≥43Gy (95%)
9	Rectum		V _{69Gy} < 15 %
10	ΡΤVΤ3	52.2	D _{95%} ≥43Gy (95%)
11	PTVN	52.2	D _{98%} ≥42 Gy (93%)
12	FemoralHeads_L/R		D _{2%} ≤ 51Gy
13	BowelBag		V _{28Gy} < 300 cm ³
14	Rectum		V _{37.5Gy} < 150 cm ³
15	Body-PTV		V _{42Gy} < 100 cm ³
16	Bladder		V _{46Gy} < 35 cm ³

Priority	Structure	Dose (Gy)	Dose-volume recommendations
1	CTVT1 (Prostate)	78Gy	D _{98%} ≥ 76 Gy (97%)
2	CTVT3 (tumor involved ves)	70Gy	D _{98%} ≥ 68 Gy (97%)
3	PTVT1	78Gy	D _{95%} ≥ 75 Gy (96%)
4	Rectum		V _{70Gy} < 20 %
5	PTVT1	78Gy	D _{98%} ≥ 74 Gy (95%)
6	PTVT2	70Gy	D _{98%} ≥ 66 Gy (94%)
7	CTVT2 (prox ves, 2cm)	50Gy	D _{98%} ≥ 47.5Gy (95%)
8	CTVN (Nodes)	50Gy	D _{98%} ≥ 47.5 Gy (95%)
9	Rectum		V _{75Gy} < 15 %
10	ΡΤVΤ3	50Gy	D _{95%} ≥ 47.5 Gy (95%)
11	PTVN	50Gy	D _{98%} ≥ 46.5 Gy (93%)
12	FemoralHeads_L/R		D _{2%} ≤ 55Gy
13	BowelBag		$V_{30Gy} < 300 \text{ cm}^3$
			$V_{40Gy} < 150 \text{ cm}^3$
			$V_{45Gy} < 100 \text{ cm}^3$
			$V_{50Gv} < 35 \text{ cm}^3$
14	Rectum		V _{60Gy} < 35 %
15	Body-PTV		D _{2%} ≤ 83 Gy (107%)
16	Bladder		D _{mean} ≤ 62 Gy (80%)

Table 2C. Dose prescription priorities for fractionation for schedule C

HDR-BOOST

Patients are anesthetized and vital functions are monitored with the patient lying in dorsal lithotomy position. HDR-BT shall be performed by introducing a thread-formed iridium-192 source into hollow steel needles perforating the perineum and placed into the prostatic gland. The needles are inserted by transrectal ultrasound guidance. The treatment plan should encompass the prostatic gland (CTVT1) and 2 mm isotrope margin to the PTVT1.

Table 3

Risk organ	Brachy regime	Constraints	Fraction dose/fraction	EQD2 HDR (α/β = 3)	EQD2 HDR-External RT $(\alpha/\beta = 3)$
Urethra	10 Gy x 2	Max. 11.5 Gy to 0.1 cc	11.5 Gy / 2	66.7 Gy	116.7 Gy
Urethra	15 Gy x 1	Max 16.8 Gy to 0.1 cc	16.8 Gy / 1	66.5 Gy	116.5 Gy
Urethra	10 Gy x 2	Max point dose 12 Gy	12 Gy / 2	72 Gy	122 Gy
Urethra	15 Gy x 1	Max point dose 17.5 Gy	17.5 Gy / 1	71.8 Gy	121.8 Gy
Urethra	10 Gy x 2	Max 7.6 Gy to 2cc	7.6 Gy / 2	32.2 Gy	82.2 Gy
Rectum	15 Gy x 1	Max 11.3 Gy to 2cc*	11.3 Gy / 1	32.3 Gy	82.3 Gy
Rectum	10 Gy x 2	Max 6.6 Gy	6.6 Gy / 2	25.2 Gy	75.3 Gy

*Check visually =< 60% of rectal mucosa to 2cc

EQD2 for rectum and urethra (a/b=3Gy) is 50.8 Gy for 14.5 Gy x 1 and 54.0 Gy for 15.0 Gy x 1.

POST-OPERATIVE RADIOTHERAPY

ENDOCRINE THERAPY

150 mg of bicalutamide is administered for 18 months during and after post-operative radiotherapy, starting up to two weeks before the start of radiation treatment but after profylactic breast irradiation. PATIENT POSITION AND FIXATION

The patient will be treated in supine position. The position must be the same during planning, simulation and treatment.

The patient should be immobilized according to the standard procedures of each participating centre. The type of fixation device/technique shall be reported in the RTQA-report

PATIENT DATA ACQUISITION

A CT based simulation shall be made in the treatment position for all cases, on a flat table top and with the patient in his fixation device. CT scanning shall be performed with a slice thickness of maximum 3 mm. As an option, MR images that are co-registered with the planning CT images may also be used.

In patients with extremely filled rectum (> 4 cm) due to faeces or gas, new planning CT/MR should be performed prior to treatment planning. The bladder should be comfortably filled. Images will be obtained from at least the lower end of the sacroiliacal joints to 10 mm below the tuberositas ischii.

Delineation of target volumes and organs at risk (OAR) must be done on CT images, or together with MR images appropriately co-registered with planning CT images. RT will be delivered with megavoltage equipment at energies >= 6 MV, with daily fractions of 2 Gy/5 days per week.

TARGET VOLUMES AND ORGANS-AT-RISK (OAR) VOLUMES

The definition of volumes follows the recommendations made by ICRU in Report 50 and in the supplementary ICRU Report 62 and in ICRU Report 83 for photon beam therapy.

TARGET

Clinical target volume prostate bed CTVT

The CTVT will include the prostate bed in all patients.

Information which may be used to define the prostate bed CTV includes: Histopathologic information of prostate size and tumor extent to specific boundaries of the surgical resection, pre-operative imaging e.g. pelvic CT/MRI studies and post-operative anatomy on planning CT scan.

The definition of the prostate bed CTVT is based on the estimated location of the pre-operative prostate volume plus sites of possible microscopic tumor extension, plus the extent of the surgical bed, and should normally include any surgical clips provided that the normal-tissue dose-constraints are satisfied. The following areas are at the greatest risk for relapse after prostatectomy and should therefore be included:

Centrally: the urethra-vesical anastomosis

Cranially: the bladder neck

Posteriorly: up to but not including the outer rectal wall, cranially including the most posterior part of the bladder neck

- Caudally: including the apex (15 mm cranially from the penile bulb)
- Laterally: up to the neurovascular bundles (if removed up to the ilio-obturatic muscles)
- Anteriorly: including the anastomosis and the urethral axis.

The original volume of seminal vesicles (including any residual seminal vesicle tissue post-op) will not be considered target if they were not pathologically involved with tumor. If there was pathologic involvement of the seminal vesicles, then the seminal vesicles will be considered target.

We recommend the use one of the following existing published consensus guidelines for construction of CTVT:

- The European Organization for Research and Treatment of Cancer (EORTC) guidelines
- The Faculty of Radiation Oncology Genito-Urinary Group (FROGG)
- The Radiation Therapy Oncology Group (RTOG)

Planning target volume prostate bed PTVT

The planning target volume (PTVT) will add 0.5 - 1.0 cm in all directions, for day-to-day variation in set up and for CTVT motion. Daily image guidance is mandatory. The maximum PTVT is 500 ccm.

ORGANS AT RISK

- The following OARs shall be delineated (structure name within parenthesis):
 - Rectum (Rectum), delineated according to the recommendations by QUANTEC²: "The rectum should be segmented from above the anal verge to the turn into the sigmoid colon, including the rectal contents." "The superior limit is where the bowel moves anteriorly, close to the inferior level of the sacroiliac joints, and the inferior limit is commonly at the bottom of the ischial tuberosities."
 - Anal canal (AnalCanal) shall be outlined as a separate volume with a default extension from the distal end of the anal canal with a caudocranial direction of 4 cm.
 - The urinary bladder (Bladder) shall be outlined as the outer contour of the bladder, i.e. including the muscle wall.
 - The penile bulb (PenileBulb) is defined as the oval-shaped area bounded by the crura, corpora spongiosum and the levator ani muscles (the most proximal portion of the penis) sitting approximately 1-1.5 cm caudal to the prostate. The penile bulb appears as a hyperintense oval-shaped structure on T2-weighted MR images and thus MR-based segmentation is recommended.
 - The femoral heads (FemoralHead_L and FemoralHead_R) are delineated circumferentially not including the femur neck.

Structure names in treatment planning system, Same as for primary radiotherapy treatment, se above.

RADIATION TREATMENT TECHNIQUE

The radiation treatment shall be given with external photon beam therapy with 3D-CRT and/or IMRT (VMAT) techniques. It is left to each centre to decide upon the optimal technique (number of beams, beam weights, beam angles, beam shaping, etc.).

The position shall be verified prior to every fraction with electronic kV or MV portal imaging or x-ray volumetric imaging (cone beam CT). Guidance can either be done using surgical clips or bony structures.

DOSE SPECIFICATIONS

Prescribed average dose to CTV-PB will be 66-70 Gy in 33-35 fractions over 6.5-7.0 weeks. Megavoltage equipment is required with effective photon energies ≥6MV. Minimum source-to-axis distance is 100cm.

² Michalski JM, Gay H, Jackson A, Tucker SL, Deasy JO. Radiation dose-volume effects in radiation-induced rectal injury. Int J Radiat Oncol Biol Phys. 2010 Mar 1;76(3 Suppl):S123-9. doi: 10.1016/j.ijrobp.2009.03.078.

The minimal dose to the PTV shall not be less than 95% of the prescribed dose; the maximum, not more than 105% of the prescribed dose.

Priority	Volume	Prescribed dose	
1	CTVT	D _{min} ≥ 95% D _{min} ≥ 66,5 Gy	The minimum dose to CTV-PB shall be greater than or equal to 95% of the prescribed dose, i.e. $D_{mean, PTV-P}$.
2	ΡΤντ	V _{95%} ≥ 95% V _{66,5Gy} ≥ 95%	The 95% isodose shall cover at least 95% of PTV-PB.
3	Rectum	V _{90%} ≤ 15% V63 _{Gy} ≤ 15%	Less than 15 % of the outlined rectal volume should receive doses greater than 90% of the prescribed dose.
4	ΡΤΥΤ	D _{98%} ≥ 90% D _{98%} ≥ 66 Gy	The "near minimum dose" to PTV-PB should be greater than or equal to 90% of the prescribed dose.
5	Rectum	V _{75%} ≤ 35% V52,5 _{Gy} ≤ 35%	Less than 35 % of the outlined rectal volume should receive doses greater than 75% of the prescribed dose.
6	Femoral heads_L/R	D _{2%} ≤ 75% D _{2%} ≤ 52,5 Gy	The near maximum dose to the femoral heads should be less than or equal to 75% of the prescribed dose.
7	Rectum	V _{70%} ≤ 50% V _{49Gy} ≤ 50%	Less than 50 % of the outlined rectal volume should receive doses greater than 70% of the prescribed dose.
8	Bladder (Bladder- CTVT)	V _{90%} ≤ 50% V _{65Gy} ≤ 50%	Less than 50 % of the outlined Bladder- CTV-PB volume should receive doses greater than 90% of the prescribed dose.
9	Bladder (Bladder- CTVT)	V _{90%} ≤ 70% V _{42Gy} ≤ 70%	Less than 70 % of the outlined Bladder- CTV-PB volume should receive doses greater than 60% of the prescribed dose.
10	Penile Bulb	Registered	NA
11	Body	D _{2%} ≤ 107% D _{2%} ≤ 75 Gy	The maximum global dose should be less than or equal to 107% of the prescribed dose.

 Table 4. Tolerance doses of risk organs and dose constraints

QUALITY ASSURANCE

(Applicable to both primary and postoperative radiotherapy)

A working group will be assigned for collecting treatment and verification data to ensure that the physical quality of the treatments follows the study protocol.

Radiotherapy related treatment information and other relevant documentation for each patient shall be sent to the QA-group at completion of radiotherapy.

Quality audits may be performed by the QA-group during the trial.

The aim of the QA is to ensure uniformity of all radiotherapy data for every patient in order to answer the questions in the trial. Specifically this means:

- To establish a uniform instruction of radiotherapy details,

- To evaluate compliance for all patients with the instructions of the radiotherapy details, and
- To enable a correct evaluation of the endpoints in the trial.

The QA procedure has two parts;

- Dummy run, and

- Individual patient evaluation checks.

DUMMY RUN PROCEDURE

A dummy run will be performed before the start of the patient trial.

The dummy run procedure consists of two separate parts:

- 1. Delineation of structures (targets and organs at risk)
- 2. Treatment planning of predefined target volumes

The first part is dedicated to *definition of volumes*. CT images of a prostate cancer patient will be sent from RTQA-office. The target volumes (CTV and PTV) and the organs at risk (rectum, anal canal, urinary bladder, small bowel, penile bulb and femoral heads) shall be delineated on the transversal CT slices according to the study protocol. The CT images and delineated structures shall be sent back to the RTQA-office for evaluation.

The second part is dedicated to *treatment planning*. Each institution shall make a treatment plan for the radiotherapy. The CT images, structures, plan, and dose data together with dose volume histograms (DVH) for all structures shall be sent back to the RTQA-office for evaluation.

The dummy run has to be performed and evaluated by the RTQA team before the centre starts to include patients.

Detailed practical information of the dummy run procedure will be sent out separately to each participating centre.

INDIVIDUAL PATIENT EVALUATION CHECKS OF THE RADIOTHERAPY TREATMENT

A final treatment evaluation of every single patient shall be performed after completion of radiotherapy. The following parameters will be checked and evaluated at the RTQA-office:

Patient immobilization

CT scanning (number of slices, slice thickness)

Volumes of targets (CTV and PTV) and organs at risk (rectum, anal canal, urinary bladder, small bowel, penile bulb and femoral heads)

3D treatment planning (beam arrangements, beam shaping, beam quality, etc.)

Dose prescription

Dose volume histograms

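### Schedule D names the target of its 2.16–2.2 Gy fraction in three different ways, leaving open whether the seminal vesicles are in it

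*Protocol*

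**What the plan says.** The volume section of Appendix B separates three tumour-related targets for primary external beam treatment. CTVT1 is the prostate with any extra-capsular growth. CTVT2 "shall include the proximal 2 cm of the seminal vesicles". CTVT3 is any vesicle involved by tumour, to be contoured on its own. The same list labels the pelvic nodes CTVT4.

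Table 1 of Appendix B gives schedules A, B and C one row for each tumour target and one for the nodes. The schedule A row for proximal vesicles, for example, reads "PTVT2 25 2.00 50.0 (50.0", with the EQD2 in brackets.

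Schedule D has two rows only: an unnumbered PTVT ("35 2.2 77.0 (78.0") and PTVN. Two pieces of text follow:

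- The sentence under the table: "the treatment regime will be 2,2 Gy to the prostate (PTVT4"), with 1.6 Gy per fraction to the elective nodes. It does not mention vesicles.
- The calculation for the simultaneous integrated boost: "Prostate and vesiculae seminales" receive "2,16Gy-2.2Gy/35f Nominal dose 76-77Gy", with a printed EQD2 of 78–80 Gy. It does not separate involved from uninvolved vesicles.

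The section on planning aims says that fractionation schedules biologically equivalent to 78 Gy "are allowed with dose prescriptions comparable to schedules given in Table 1". Table 1 is therefore the benchmark for what a site may give.

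**The concern.** Three adjacent places describe one 35-fraction regimen, and they do not say the same thing about the vesicles. A planner who follows the sentence under Table 1 finds a prostate dose and a nodal dose and nothing for CTVT2 or CTVT3, although the volume section requires both to be considered. A planner who follows the boost calculation gives the vesicles the full prostate fraction, whether or not they contain tumour.

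This is a conflict in a prescription rule, not detail left for another document. The trial enrols T3 disease and its MRI reporting template records seminal vesicle invasion, so the vesicle question will recur. Two sites could both follow schedule D in good faith and treat this volume very differently within the reference arm. The radiotherapy QA process is meant to check each patient's volumes and prescription, and here it would have no single standard to check against. The planned subgroup analysis by type of radiotherapy would also be harder to interpret if one schedule covered two practices.

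**Working it through.** **Formula.** EQD2 = n × d × (d + 3) / (2 + 3), where n is the number of fractions, d is the dose per fraction in Gy, and alpha/beta is 3 Gy. The sentence under Table 1 states this alpha/beta ("BED2= 78 Gy, alfa/beta=3").

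**The protocol's own figure for schedule D.**
- 35 × 2.16 = 75.6 Gy; 75.6 × 5.16/5 = 78.0 Gy.
- 35 × 2.20 = 77.0 Gy; 77.0 × 5.20/5 = 80.1 Gy.

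The range of 78–80 Gy printed in the boost calculation is reproduced. Table 1 and the sentence below it attach 78 Gy to 2.2 Gy per fraction, but that value belongs to 2.16 Gy; 2.2 Gy gives 80.1 Gy. This should be tidied in the same correction.

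**Vesicle doses in schedules A–C, from the Table 1 inputs.**

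| Volume | Schedule | Inputs | Recomputed EQD2 | Printed EQD2 |
|---|---|---|---|---|
| Proximal (PTVT2) | A | 25 × 2.00 = 50.0 Gy | 50.0 | 50.0 |
| Proximal (PTVT2) | B | 29 × 1.80 = 52.2 Gy | 52.2 × 4.8/5 = 50.1 | 50.1 |
| Proximal (PTVT2) | C | 58.4 Gy in 39, d = 1.497 | 58.4 × 4.497/5 = 52.5 | 50.0 |
| Engaged (PTVT3) | A | 35 × 2.00 = 70.0 Gy | 70.0 | 70.0 |
| Engaged (PTVT3) | B | 29 × 2.30 = 66.7 Gy | 66.7 × 5.3/5 = 70.7 | 70.7 |
| Engaged (PTVT3) | C | 72.8 Gy in 39, d = 1.867 | 72.8 × 4.867/5 = 70.9 | 70.0 |

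Schedule C's printed fraction doses are rounded. At exactly 1.5 Gy, its proximal figure is 58.5 × 4.5/5 = 52.65 Gy.

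**Difference for proximal vesicles, if schedule D includes them.**
- On printed EQD2 values for A–C: from 78.0 − 50.1 = 27.9 Gy to 80.1 − 50.0 = 30.1 Gy.
- On recomputed values: from 78.0 − 52.65 = 25.4 Gy to 80.1 − 50.0 = 30.1 Gy.

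**Difference for engaged vesicles, on the same reading.** From 78.0 − 70.9 = 7.1 Gy to 80.1 − 70.0 = 10.1 Gy.

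**If schedule D covers the prostate only.** No dose is stated for either vesicle volume, so no difference can be computed.

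**Does anything else settle the target?**
- The primary treatment volume list has PTVT1, PTVT2, PTVT3 and PTVN. It has no plain PTVT and no PTVT4.
- The T4 label in that list belongs to the pelvic nodes, whereas the schedule D sentence uses it for the prostate.
- A plain PTVT is defined only in the post-operative section, where it means the prostate bed.
- Tables 2A–2C give target coverage for schedules A–C only. The boost block lists limits for organs at risk but has no coverage rows for targets.

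Nothing in the protocol decides between the two readings.

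**The case against.** The best defence is that schedule D is a two-level plan: one combined tumour volume plus nodes. The unnumbered PTVT fits this, and so does the boost calculation; the word prostate in the sentence under Table 1 would then be shorthand. On this reading the vesicles do have a dose. It is plausible and perhaps the more natural reading, but the protocol does not say so, and the sentence ties the 2.2 Gy volume to the prostate under a label that the volume list gives to the nodes. If a digit was lost from the table cell in the text copy, the conflict between the sentence and the calculation would remain.

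The general contouring instructions apply to schedule D too, so the proximal 2 cm and any engaged vesicle are still outlined. That is right, but contouring does not set a dose.

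Several further objections stand and limit the point. A reader might infer that schedule D is wrong because its vesicle dose departs from A–C. The documents do not support that: nothing requires equal vesicle doses across schedules, and the difference may be a design choice. A reader might also infer that D must be given separate PTVT2 and PTVT3 rows, but that would presume a prescription structure which a combined-volume plan does not need. Nor do the documents show excess rectal or bladder harm: schedule D carries its own organ limits, and no toxicity estimate is available. Finally, the protocol already requires a planning dummy run before a site includes patients, and a check of volumes, prescription and dose-volume histograms for every patient. An additional recording duty would largely repeat this.

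**Conclusion.** The point holds as an inconsistency in the named target of schedule D. Depending on which line is followed, the seminal vesicles get an EQD2 of about 78–80 Gy irrespective of involvement, or have no stated dose. Against A–C, the first reading is about 25–30 Gy higher for proximal vesicles and about 7–10 Gy higher for engaged ones. These figures rest on alpha/beta of 3 Gy, which the protocol uses, and on the Table 1 inputs. The proximal comparator is about 50 Gy as printed, but 52.5 Gy on schedule C's own total dose and fraction number.

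The A–C figures show why the ambiguity matters; they do not show that schedule D is in error. A bias in cause-specific survival cannot be inferred either. The share of men on schedule D is not given, and randomization is stratified by site, which helps to balance site technique between arms, although it does not make the reference treatment uniform. The point merits correction because two readings of a prescription rule differ materially in a T3 population.

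**What to change.** In Appendix B:

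1. Reconcile the schedule D row of Table 1, the sentence below it and the boost calculation, so that all three name the same target, the same fraction dose or range, and the EQD2 that follows from it.
2. Define PTVT and PTVT4 in terms of the volumes already listed (prostate, proximal vesicles, tumour-engaged vesicles, nodes), or replace those labels.
3. State which volumes the 2.16–2.2 Gy fraction covers, and how the proximal and the tumour-engaged vesicle volumes are handled under schedule D. If the difference from A–C is intended, say so in a line.
4. Notify sites and the radiotherapy QA group, so that the existing dummy run and individual checks use one reference.

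The sponsor's radiotherapy group must decide the dose and the volume structure; this review proposes neither. The cost is an appendix correction and a note to sites, with no additional patients or procedures.
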